10.1.7. Source Documents

- Source documents provide evidence for the existence of the participant and substantiate the integrity of the data collected. Source documents are filed at the investigator's site.
- Data reported on the CRF or entered in the eCRF that are transcribed from source documents must be consistent with the source documents or the discrepancies must be explained. The investigator may need to request previous medical records or transfer records, depending on the study. Also, current medical records must be available.
- Definition of what constitutes source data can be found in Source Document Agreement.

10.1.8. Study and Site Closure

GSK or its designee reserves the right to close the study site or terminate the study at any time for any reason at the sole discretion of GSK. Study sites will be closed upon study completion. A study site is considered closed when all required documents and study supplies have been collected and a study-site closure visit has been performed.

The investigator may initiate study-site closure at any time, provided there is reasonable cause and sufficient notice is given in advance of the intended termination.

Reasons for the early closure of a study site by the sponsor or investigator may include but are not limited to:

- Failure of the investigator to comply with the protocol, the requirements of the IRB/IEC or local health authorities, the sponsor's procedures, or GCP guidelines
- Inadequate recruitment of participants by the investigator
- Discontinuation of further study intervention development

10.1.9. Publication Policy

- The results of this study may be published or presented at scientific meetings. If this is foreseen, the investigator agrees to submit all manuscripts or abstracts to the sponsor before submission. This allows the sponsor to protect proprietary information and to provide comments.
- The sponsor will comply with the requirements for publication of study results. In accordance with standard editorial and ethical practice, the sponsor will generally support publication of multicentre studies only in their entirety and not as individual site data. In this case, a coordinating investigator will be designated by mutual agreement.
- Authorship will be determined by mutual agreement and in line with International Committee of Medical Journal Editors authorship requirements.

10.2. Appendix 2: Clinical Laboratory Tests

- The tests detailed in [Table 5](#) will be performed by the local laboratory.
- Protocol-specific requirements for inclusion or exclusion of participants are detailed in Section [5](#) of the protocol.
- Additional tests may be performed at any time during the study as determined necessary by the investigator or required by local regulations.

Table 5 Protocol-Required Safety Laboratory Assessments

Laboratory Assessments	Parameters			
Haematology	Platelet Count	RBC Indices: MCV MCH %Reticulocytes	WBC count with Differential: Neutrophils Lymphocytes Monocytes Eosinophils Basophils	
	RBC Count			
	Haemoglobin			
	Haematocrit			
Clinical Chemistry ¹	BUN	Potassium	Aspartate Aminotransferase (AST)/ Serum Glutamic-Oxaloacetic Transaminase (SGOT)	Total and direct bilirubin
	Creatinine	Sodium	Alanine Aminotransferase (ALT)/ Serum Glutamic-Pyruvic Transaminase (SGPT)	Total Protein
	Glucose (fasting at screening)	Calcium	Alkaline phosphatase	
Routine Urinalysis	
 • Specific gravity • pH, glucose, protein, blood, ketones, by dipstick • Microscopic examination (if blood or protein is abnormal) 			
Other Screening (or Pre-dose) Tests	
 • Follicle-stimulating hormone (as needed in women of non-childbearing potential only) • Urine drug screen (to include at minimum: amphetamines, barbiturates, cocaine, opiates, cannabinoids and benzodiazepines) • Serology (HIV antibody, hepatitis B surface antigen [HBsAg], and hepatitis C virus antibody) 			

NOTES :

1. Details of liver chemistry stopping criteria and required actions and follow-up assessments after liver stopping or monitoring event are given in Section 7.1 and [Appendix 5](#). All events of ALT $\geq 3 \times$ upper limit of normal (ULN) and bilirubin $\geq 2 \times$ ULN ($>35\%$ direct bilirubin) or ALT $\geq 3 \times$ ULN and international normalized ratio (INR) >1.5 , if INR measured, which may indicate severe liver injury (possible Hy's Law), must be reported as an SAE (excluding studies of hepatic impairment or cirrhosis).

10.3. Appendix 3: Adverse Events: Definitions and Procedures for Recording, Evaluating, Follow-up, and Reporting

10.3.1. Definition of AE

AE Definition

• An AE is any untoward medical occurrence in a clinical study participant, temporally associated with the use of a study intervention, whether or not considered related to the study intervention.• NOTE: An AE can therefore be any unfavorable and unintended sign (including an abnormal laboratory finding), symptom, or disease (new or exacerbated) temporally associated with the use of a study intervention.

Events Meeting the AE Definition

• Any abnormal laboratory test results (hematology, clinical chemistry, or urinalysis) or other safety assessments (e.g., ECG, radiological scans, vital signs measurements), including those that worsen from baseline, considered clinically significant in the medical and scientific judgment of the investigator (i.e., not related to progression of underlying disease).• Exacerbation of a chronic or intermittent pre-existing condition including either an increase in frequency and/or intensity of the condition.• New conditions detected or diagnosed after study intervention administration even though it may have been present before the start of the study.• Signs, symptoms, or the clinical sequelae of a suspected drug-drug interaction.• Signs, symptoms, or the clinical sequelae of a suspected overdose of either study intervention or a concomitant medication. Overdose per se will not be reported as an AE/SAE unless it is an intentional overdose taken with possible suicidal/self-harming intent. Such overdoses should be reported regardless of sequelae.

Events NOT Meeting the AE Definition

• Any clinically significant abnormal laboratory findings or other abnormal safety assessments which are associated with the underlying disease, unless judged by the investigator to be more severe than expected for the participant's condition.• The disease/disorder being studied or expected progression, signs, or symptoms of the disease/disorder being studied, unless more severe than expected for the participant's condition.• Medical or surgical procedure (e.g., endoscopy, appendectomy): the condition that leads to the procedure is the AE.

- Situations in which an untoward medical occurrence did not occur (social and/or convenience admission to a hospital).
- Anticipated day-to-day fluctuations of pre-existing disease(s) or condition(s) present or detected at the start of the study that do not worsen.

10.3.2. Definition of SAE

If an event is not an AE per definition above, then it cannot be an SAE even if serious conditions are met (e.g., hospitalization for signs/symptoms of the disease under study, death due to progression of disease).

A SAE is defined as any untoward medical occurrence that, at any dose:

- Results in death
- Is life-threatening

The term 'life-threatening' in the definition of 'serious' refers to an event in which the participant was at risk of death at the time of the event. It does not refer to an event, which hypothetically might have caused death, if it were more severe.

Requires inpatient hospitalization or prolongation of existing hospitalization

In general, hospitalization signifies that the participant has been detained (usually involving at least an overnight stay) at the hospital or emergency ward for observation and/or treatment that would not have been appropriate in the physician's office or outpatient setting. Complications that occur during hospitalization are AE. If a complication prolongs hospitalization or fulfils any other serious criteria, the event is serious. When in doubt as to whether "hospitalization" occurred or was necessary, the AE should be considered serious.

Hospitalization for elective treatment of a pre-existing condition that did not worsen from baseline is not considered an AE.

Results in persistent disability/incapacity

- The term disability means a substantial disruption of a person's ability to conduct normal life functions.
- This definition is not intended to include experiences of relatively minor medical significance such as uncomplicated headache, nausea, vomiting, diarrhea, influenza, and accidental trauma (eg, sprained ankle) which may interfere with or prevent everyday life functions but do not constitute a substantial disruption.

Is a congenital anomaly/birth defect

Other situations:

- Medical or scientific judgment should be exercised in deciding whether SAE reporting is appropriate in other situations such as important medical events that may

not be immediately life-threatening or result in death or hospitalization but may jeopardize the participant or may require medical or surgical intervention to prevent one of the other outcomes listed in the above definition. These events should usually be considered serious.

Examples of such events include invasive or malignant cancers, intensive treatment in an emergency room or at home for allergic bronchospasm, blood dyscrasias or convulsions that do not result in hospitalization, or development of drug dependency or drug abuse.

10.3.3. Recording and Follow-Up of AE and SAE

AE and SAE Recording

- When an AE/SAE occurs, it is the responsibility of the investigator to review all documentation (eg, hospital progress notes, laboratory, and diagnostics reports) related to the event.
- The investigator will then record all relevant AE/SAE information in the CRF.
- It is **not** acceptable for the investigator to send photocopies of the participant's medical records to GSK in lieu of completion of the GSK /AE/SAE CRF page.
- There may be instances when copies of medical records for certain cases are requested by GSK. In this case, all participant identifiers, with the exception of the participant number, will be redacted on the copies of the medical records before submission to GSK.
- The investigator will attempt to establish a diagnosis of the event based on signs, symptoms, and/or other clinical information. Whenever possible, the diagnosis (not the individual signs/symptoms) will be documented as the AE/SAE.

Assessment of Intensity

The investigator will make an assessment of intensity for each AE and SAE reported during the study and assign it to 1 of the following categories:

- Mild: An event that is easily tolerated by the participant, causing minimal discomfort and not interfering with everyday activities.
- Moderate: An event that causes sufficient discomfort and interferes with normal everyday activities.
- Severe: An event that prevents normal everyday activities. An AE that is assessed as severe should not be confused with an SAE. Severe is a category utilized for rating the intensity of an event; and both AE and SAE can be assessed as severe.

An event is defined as 'serious' when it meets at least 1 of the predefined outcomes as described in the definition of an SAE, NOT when it is rated as severe.

Assessment of Causality

- The investigator is obligated to assess the relationship between study intervention and each occurrence of each AE/SAE.
- A "reasonable possibility" of a relationship conveys that there are facts, evidence, and/or arguments to suggest a causal relationship, rather than a relationship cannot be ruled out.
- The investigator will use clinical judgment to determine the relationship.
- Alternative causes, such as underlying disease(s), concomitant therapy, and other risk factors, as well as the temporal relationship of the event to study intervention administration will be considered and investigated.
- The investigator will also consult the Investigator's Brochure (IB) and/or Product Information, for marketed products, in his/her assessment.
- For each AE/SAE, the investigator **must** document in the medical notes that he/she has reviewed the AE/SAE and has provided an assessment of causality.
- There may be situations in which an SAE has occurred and the investigator has minimal information to include in the initial report to GSK. However, **it is very important that the investigator always make an assessment of causality for every event before the initial transmission of the SAE data to GSK.**
- The investigator may change his/her opinion of causality in light of follow-up information and send an SAE follow-up report with the updated causality assessment.
- The causality assessment is one of the criteria used when determining regulatory reporting requirements.

Follow-up of AE and SAE

- The investigator is obligated to perform or arrange for the conduct of supplemental measurements and/or evaluations as medically indicated or as requested by GSK to elucidate the nature and/or causality of the AE or SAE as fully as possible. This may include additional laboratory tests or investigations, histopathological examinations, or consultation with other health care professionals.
- If a participant dies during participation in the study or during a recognized follow-up period, the investigator will provide GSK with a copy of any post-mortem findings including histopathology.
- New or updated information will be recorded in the originally completed CRF.
- The investigator will submit any updated SAE data to GSK within 24 hours of receipt of the information.

10.3.4. Reporting of SAE to GSK

SAE Reporting to GSK via Electronic Data Collection Tool

- The primary mechanism for reporting SAE to GSK will be the electronic data collection tool.
- If the electronic system is unavailable, then the site will use the paper SAE data collection tool (see next section) in order to report the event within 24 hours.
- The site will enter the SAE data into the electronic system as soon as it becomes available.
- The investigator or medically-qualified sub-investigator must show evidence within the eCRF (e.g., check review box, signature, etc.) of review and verification of the relationship of each SAE to IP/study participation (causality) within 72 hours of SAE entry into the eCRF.
- After the study is completed at a given site, the electronic data collection tool will be taken off-line to prevent the entry of new data or changes to existing data.
- If a site receives a report of a new SAE from a study participant or receives updated data on a previously reported SAE after the electronic data collection tool has been taken off-line, then the site can report this information on a paper SAE form (see next section) or to the medical monitor by telephone.
- Contacts for SAE reporting can be found in SRM.

SAE Reporting to GSK via Paper CRF

- Facsimile transmission of the SAE paper CRF is the preferred method to transmit this information to the medical monitor.
- In rare circumstances and in the absence of facsimile equipment, notification by telephone is acceptable with a copy of the SAE data collection tool sent by overnight mail or courier service.
- Initial notification via telephone does not replace the need for the investigator to complete and sign the SAE CRF pages within the designated reporting time frames.
- Contacts for SAE reporting can be found in SRM.

10.4. Appendix 4: Contraceptive Guidance and Collection of Pregnancy Information

10.4.1. Definitions:

Women in the following categories are not considered WOCBP

1. Premenarchal
2. Premenopausal female with 1 of the following:
 - Documented hysterectomy
 - Documented bilateral salpingectomy
 - Documented bilateral oophorectomy

For individuals with permanent infertility due to an alternate medical cause other than the above, (e.g., mullerian agenesis, androgen insensitivity), investigator discretion should be applied to determining study entry.

Note: Documentation can come from the site personnel's: review of the participant's medical records, medical examination, or medical history interview.

3. Postmenopausal female
 - A postmenopausal state is defined as no menses for 12 months without an alternative medical cause.
 - A high follicle stimulating hormone (FSH) level in the postmenopausal range may be used to confirm a postmenopausal state in women not using hormonal contraception or hormonal replacement therapy (HRT). However, in the absence of 12 months of amenorrhea, confirmation with more than one FSH measurement in the postmenopausal range is required.
 - Females on HRT and whose menopausal status is in doubt will be required to use one of the non-oestrogen hormonal highly effective contraception methods if they wish to continue their HRT during the study. Otherwise, they must discontinue HRT to allow confirmation of postmenopausal status before study enrolment.

10.4.2. Contraception Guidance:

CONTRACEPTIVES ^a REQUIRED DURING THE STUDY FOR FEMALE PARTNERS OF MALE PARTICIPANTS:	

 • Highly Effective Methods ^b That Have Low User Dependency Failure rate of <1% per year when used consistently and correctly. 	

 • Implantable progestogen-only hormone contraception associated with inhibition of ovulation^c 	

 • Intrauterine device (IUD) 	

 • Intrauterine hormone-releasing system (IUS)^c 	

 • Bilateral tubal occlusion 	

 • Highly Effective Methods ^b That Are User Dependent Failure rate of <1% per year when used consistently and correctly. 	

 • Combined (estrogen- and progestogen-containing) hormonal contraception associated with inhibition of ovulation 
 • oral • intravaginal • transdermal • injectable 	

 • Progestogen-only hormone contraception associated with inhibition of ovulation 
 • oral • injectable 	

a. Contraceptive use by men or women should be consistent with local regulations regarding the use of contraceptive methods for those participating in clinical studies.
 
b. Failure rate of <1% per year when used consistently and correctly. Typical use failure rates differ from those when used consistently and correctly.
 
Note: Periodic abstinence (calendar, sympto-thermal, post-ovulation methods), withdrawal (coitus interruptus), spermicides only, and lactational amenorrhoea method (LAM) are not acceptable methods of contraception. Male condom and female condom should not be used together (due to risk of failure with friction)
	

10.4.3. Collection of Pregnancy Information:

Male participants with partners who become pregnant

- Investigator will attempt to collect pregnancy information on any male participant's female partner of a male study participant who becomes pregnant while participating in this study.
- After obtaining the necessary signed informed consent from the pregnant female partner directly, the investigator will record pregnancy information on the appropriate form and submit it to GSK within 24 hours of learning of the partner's pregnancy.
- The female partner will also be followed to determine the outcome of the pregnancy. Information on the status of the mother and child will be forwarded to GSK.

- Generally, follow-up will be no longer than 6 to 8 weeks following the estimated delivery date. Any termination of the pregnancy will be reported regardless of foetal status (presence or absence of anomalies) or indication for procedure.

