1.3. Schedule of Activities (SoA)

1.3.1. Screening and Follow-up Schedule of Activities

Procedure	Screening ¹ (up to 28 days before first dose)	Follow up/Early Withdrawal (7-14 days post last dose)	Notes
Informed consent	X		
Inclusion and exclusion criteria	X		
Demography	X		
Medical history (includes substance usage)	X		Substances: Drugs, Alcohol, tobacco
Full physical exam, including height and weight	X		
Brief physical exam		X	
HIV, Hep B and Hep C screen	X		
Clinical chemistry, haematology and urinalysis	X	X	Only screening tests need to be fasted
FSH	X		Required only in women to confirm postmenopausal status
Alcohol breath test	X		
Urine drugs test	X		
Vital signs (blood pressure, heart rate and temperature)	X	X	Triuplicate blood pressure and heart rate required at screening.
12-lead ECG	X	X	Triuplicate ECG required at screening.
Concomitant Medication review	X	X	Con meds before dosing can be recorded in medical history
AE/SAE review	X	X	Refer to Section 8.3.1

1. Screening assessments may be conducted at multiple visits, if required.

1.3.2. Treatment Periods 1, 2 and 3 (minimum of 7 days washout between doses)

Procedure	Day -1	Day 1 (hours)												Day 2	Day 3	Day 4	Notes
		Pre-dose	0	0.5	1	1.5	2	2.5	4	8	12	18	24	36	48	72	
Clinic Visits																	
Out-patient Visit																X	
Admission to clinic	X																
Discharge from clinic															X		If more convenient for participants, they can remain in the unit until 72 h, at the discretion of the investigator
Study Intervention																	
Randomisation		X															Can be done on Day -1 or Pre-dose Day 1. Only in Treatment Period 1
Study Intervention			X														Fasted from midnight until 4 h post-dose, except for water, allowed ad libitum, except for 1 h before and after dosing
Safety Assessments																	
Vital signs (blood pressure, heart rate and temperature)		X		X	X		X		X	X	X		X		X	X	Triplicate pre-dose. Single measurements at other timepoints, unless out of range, then triplicates should be performed
12-lead ECG		X			X		X		X		X		X			X	
Clinical chemistry, haematology and urinalysis	X														X		Fasting not required
Brief physical examination	X																
Alcohol breath test	X																
Urine drugs test	X																

Procedure	Day -1	Day 1 (hours)												Day 2		Day 3		Day 4	Notes
		Pre-dose	0	0.5	1	1.5	2	2.5	4	8	12	18	24	36	48	72			

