2.3.1. Risk Assessment

Potential Risk of Clinical Significance	Summary of Data/Rationale for Risk	Mitigation Strategy
Investigational Product (IP) AMB (GSK1325760)		

Identified and potential risks, from European Union Risk Management Plan (EURMP) for Volibris:
 
 • Teratogenicity • Decreased haemoglobin/haematocrit, anaemia, including anaemia requiring transfusion • Hepatotoxicity • Testicular tubular atrophy/Male infertility 
Consistent with the mechanism of action for AMB, there is a potential risk of hypotension in healthy participants.
	
 • Refer to EURMP for Volibris v8.1 (EURMP, 2019) • Refer to Volibris EMA Summary of Product Characteristics (SmPC, 2018) 	
Exclusion criteria, ongoing safety assessments, study design and medical supervision. Specifically:
 
 • The use of single doses in this study. • Exclusion of women of child bearing potential. • Exclusion of potentially anaemic participants. • Haemoglobin reduction withdrawal criterion for individual participants. • Inclusion criteria to prevent enrolment of hypotensive participants. • Hypotension withdrawal criterion for individual participants. • Laboratory assessments per protocol. • Physical assessment per protocol. • Routine vital signs per protocol. • Participants remain in the clinical unit, under medical supervision, for all doses and until completion of safety assessments at 48 hrs post dose.
Study Procedures		
Risk associated with blood draws	Fainting, mild pain, bruising, irritation or redness at phlebotomy site, may be associated with blood draws.	Experienced site staff will follow standard approaches for managing events related to blood draws.

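### Appendix 4 lets a woman on HRT with doubtful menopausal status take part on contraception, with no confirmation of status and no scheduled pregnancy test

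*Protocol*

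**What the plan says.** Teratogenicity is among the listed risks in section 2.3.1. The mitigations there are given as one list for all risks, and the one that bears most directly on teratogenicity is "Exclusion of women of child bearing potential". Criterion 5b in section 5.1 puts this into effect by admitting women only if they are not of childbearing potential under Appendix 4.

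Section 10.4.1 of Appendix 4 lists the categories of women treated as not of childbearing potential. The third category, postmenopausal women, has three bullets:

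- The first defines the state as 12 months without menses and without another medical cause.
- The second says that a high FSH "may be used to confirm a postmenopausal state in women not using hormonal contraception or hormonal replacement therapy (HRT").
- The third says "Females on HRT and whose menopausal status is in doubt will be required to use one of the non-oestrogen hormonal highly effective contraception methods". That condition is for women who choose to stay on HRT while taking part. The bullet then adds: "Otherwise, they must discontinue HRT to allow confirmation of postmenopausal status before study enrolment".

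On testing, the screening schedule in section 1.3.1 has an FSH row with the note "Required only in women to confirm postmenopausal status". Table 5 in Appendix 2 lists "Follicle-stimulating hormone (as needed in women of non-childbearing potential only"). Neither schedule of activities nor Table 5 contains a pregnancy test.

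The contraceptive table in section 10.4.2 is headed as "REQUIRED DURING THE STUDY FOR FEMALE PARTNERS OF MALE PARTICIPANTS". The pregnancy-information procedure in section 10.4.3 is headed "Male participants with partners who become pregnant".

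**The concern.** The protocol's approach to a drug with a listed teratogenic risk is to admit no woman who could become pregnant. For one group Appendix 4 replaces that with something weaker. A woman whose menopausal status is in doubt may, by definition, still be of childbearing potential. The third bullet nevertheless places her among women who are not, on condition that she uses contraception.

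Contraception is a reasonable safeguard when pregnancy testing supports it, and here nothing scheduled does. The bullet sets no lead-in period before the first dose, so even perfect use from enrolment onward would not rule out a pregnancy already present at dosing. At stake is possible fetal exposure in a healthy-volunteer study that, by section 2.3.2, offers participants no clinical benefit.

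**Working it through.** No figure in the plan has to be reproduced. The check is a cross-reading of the eligibility text and a count from the schedules.

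**Step 1: which text decides eligibility.** Criterion 5b defers to Appendix 4, so section 10.4.1 is the operative rule. The HRT bullet stands inside the list of women not of childbearing potential.

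**Step 2: what the bullet requires.** It offers two alternatives.

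| Alternative | Contraception required | Status confirmed before enrolment |
|---|---|---|
| Continue HRT during the study | Yes | Not required |
| Stop HRT | Not stated | Required |

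The word that opens the second sentence, "Otherwise, they must discontinue HRT to allow confirmation of postmenopausal status before study enrolment", ties confirmation to the second alternative only.

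**Step 3: whether a scheduled test resolves the doubt.**

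- FSH is scheduled at screening only. Screening may be spread over several visits, so more than one sample is possible. The second bullet of section 10.4.1 offers FSH confirmation only for women using neither hormonal contraception nor HRT. For a woman who stays on HRT, the number of FSH results usable under that rule is 0, however many samples are taken.
- Pregnancy tests: screening 0 + treatment periods 3 × 0 + follow-up 0 = 0. Table 5 lists none.

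**Step 4: whether other procedures cover her.**

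- The contraceptive table in section 10.4.2 is written for partners of male participants. It includes combined oestrogen-containing methods, whereas the HRT bullet asks for a method outside that group.
- In section 8.3.5, the first bullet collects pregnancies in partners only. The second bullet, on notifying the sponsor within 24 hours, is general, but it refers to Appendix 4 for the procedure. Section 10.4.3 there describes only partners.

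**Step 5: size.** The protocol gives no count of women on HRT. Assumption: 0 to 2 of the 24 randomised, most plausibly 0.

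- Share of participants: 0/24 = 0% to 2/24 = 8.3%.
- Doses to women whose status is unconfirmed: 0 × 3 = 0 to 2 × 3 = 6 single doses of 5 mg.
- Scheduled pregnancy tests covering those doses: 0 in every case.

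**The case against.** The strongest reply is that the route is closed by default. HRT is a prescription medicine. Exclusion 8 bars it before the first dose unless the investigator and the sponsor's medical monitor approve, and section 6.5 bars it through follow-up unless investigator and sponsor judge that it will not interfere. In a single-centre study of 24 people, each such woman would therefore get an individual decision. That makes the route rare, but the decision concerns the medication, and neither clause asks about fertility.

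A second reply is that the bullet merely adds contraception for women who already meet the 12-month definition, since criterion 5b still applies and section 5 forbids eligibility waivers. This reading is possible but less natural. The bullet is about women whose status is in doubt, it speaks of continuing HRT during the study, and it keeps confirmation for the other alternative. If exclusion is what the sponsor intends, the continue-HRT option has no purpose and misleads the site. Either reading calls for an edit.

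Third, other safeguards exist: single doses, a method with a stated failure rate below 1% per year, discretion under Appendix 2 to add tests, a general duty to report a pregnancy, and abnormal pregnancy outcomes classed as serious adverse events. These stand and they limit the harm. None is a scheduled check of fertility or pregnancy before a dose.

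**Conclusion.** The concern holds. Appendix 4 admits a woman whose menopausal status is unresolved, contrary to the mitigation in section 2.3.1, and no scheduled test establishes her status or excludes pregnancy before any of the three doses. The reporting duty in section 8.3.5 does reach her, but the procedure it refers to does not.

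The number affected is small: 0 to 2 of 24 on my assumption, with 0 the most likely value, and the protocol offers no figure to narrow this. The estimates, precision and conclusions of the pharmacokinetic comparison do not change. This is a point of participant safety and internal consistency. It should be corrected because the possible harm is serious and the correction is slight.

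**What to change.** Remove the option to continue HRT on contraception. Replace the third bullet under postmenopausal women in section 10.4.1 with, for example: *A woman on HRT whose menopausal status is uncertain must stop HRT and have postmenopausal status confirmed before she is enrolled; if this is not done, she is excluded.* This restores the safeguard that section 2.3.1 already claims. It costs one sentence and, at most, a slightly smaller pool of eligible women.

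If the sponsor prefers to keep the option, it needs support:

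- Add pregnancy tests at screening and before each dose to sections 1.3.1 and 1.3.2 and to Table 5: 1 + 3 = 4 tests per woman concerned, so at most 2 × 4 = 8 on the assumption above. This frequency is my proposal; no figure in the protocol sets it.
- Extend sections 8.3.5, 10.4.2 and 10.4.3 to female participants.
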